6.4.4 Safety Parameters

Quantitative data (vital signs, ECG, ECOG performance status) will be described by the following summary statistics: arithmetic mean, standard deviation, median, minimum, and maximum. These summary statistics will be presented by treatment group for the original data as well as for the difference to baseline. Frequency tables will be provided for qualitative data. Graphical displays of mean values with standard deviation will be provided.

The average of triplicate quantitative ECG parameters at all ECG time points will be used for all analyses.

Laboratory data outside the reference range will be listed and flagged with 'L' for low and 'H' for high. The incidence of laboratory data outside the reference range (low, high) will be summarized by treatment group in frequency tables.

Calcium, phosphate and the product of calcium and phosphate will be described by the following summary statistics: arithmetic mean, standard deviation, median, minimum and maximum. These summary statistics will be presented by cohort for the original data as well as for the difference to baseline (defined as the pre-dose assessment of the day being analyzed).

Graphical displays of mean values with standard deviation will be included for absolute values as well as change from baseline. The number of subjects with at least one phosphate level > 5.5 mg/dL, with at least one phosphate level > 7 mg/dL and with at least one phosphate level > 9 mg/dL will be summarized using frequency tables.

The number of subjects with at least one value > 70 mg²/dL² of the product phosphate and calcium will be summarized using frequency tables.

The incidence of laboratory toxicities will also be summarized by worst CTCAE v4.03 grade and by treatment group. Frequency tables will also be provided for the changes of worst CTCAE v4.03 grade after start of treatment versus baseline.

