4.1 General Principles

The statistical evaluation will be performed by using the software package SAS release 9.2 or higher (SAS Institute Inc., Cary, NC, USA), R release 2.4.1 or higher and BRugs release 0.3-3 or higher. All variables will be analyzed by descriptive statistical methods. The number of data available, mean, standard deviation, minimum, median, and maximum will be calculated for metric data. Frequency tables will be generated for categorical data.

Data displays will follow the standard table catalogs for oncology standards, global standards, and clinical pharmacology standards, respectively.

The pharmacokinetic parameters will be evaluated statistically in accordance with pertinent company guidelines.

The following treatment groups will be analyzed:

- Total Dose Escalation – It contains all cohorts from the escalation phase:
 - 100 mg BAY 1163877 (50 mg solution BID)
 - 200 mg BAY 1163877 (100 mg solution BID)
 - 400 mg BAY 1163877 (200 mg tablet BID)
 - 800 mg BAY 1163877 (400 mg tablet BID)
 - 1200 mg BAY 1163877 (600 mg tablet BID)
 - 1600 mg BAY 1163877 (800 mg tablet BID)
- Expansion All Comers – Expansion phase, 1600 mg BAY 1163877 (800 mg tablet BID), cancer type does not fit the categories below
- Expansion Bladder – Expansion phase, 1600 mg BAY 1163877 (800 mg tablet BID), cancer type: bladder cancer

Statistical Analysis Plan

Protocol No.: **BAY 1163877/16443**

Page: 11 of 20:

- Expansion Head & Neck – Expansion phase, 1600 mg BAY 1163877 (800 mg tablet BID), cancer type: squamous carcinoma cell head and neck
- Expansion NSCLC – Expansion Phase, 1600 mg BAY 1163877 (800 mg tablet BID), cancer type: lung adenocarcinoma / squamous cell carcinoma

The categories of region used for subgroup analysis will be derived for each subject by using the variable country (location of the respective site).

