6.1.3 Demographics and other baseline characteristics

Demographics and general baseline characteristics will be summarized by treatment group. Quantitative data will be summarized by arithmetic mean, SD, median, minimum and maximum. Frequency tables will be provided for qualitative data. Variables include sex, race, ethnicity, age (as reported on the eCRF), weight, height, body mass index (BMI), and NYHA functional class.

Baseline cancer characteristics will be summarized by treatment group. Variables include for example baseline ECOG Performance Status, number of target lesions, number of non-target lesions, cancer type, histology, status of primary tumor, stage at initial diagnosis, grading at initial diagnosis, clinical status at study entry, stage at study entry, time since initial diagnosis. Please note that the list of the above mentioned parameters is not extensive.

In addition, demographics and baseline cancer characteristics will be summarized for all subjects who signed the informed consent for FGFR testing.

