6.4.4 Safety Parameters

Quantitative data (vital signs, ECG, ECOG performance status) will be described by the following summary statistics: arithmetic mean, standard deviation, median, minimum, and maximum. These summary statistics will be presented by treatment arm and cohort for the original data as well as for the difference to baseline. Frequency tables will be provided for qualitative data. Graphical displays of mean values with standard deviation will be provided.

The average of triplicate quantitative ECG parameters at all ECG time points will be used for all analyses.

Laboratory data outside the reference range will be listed and flagged with 'L' for low and 'H' for high. The incidence of laboratory data outside the reference range (low, high) will be summarized by treatment arm and cohort in frequency tables.

Calcium, phosphate and the product of calcium and phosphate will be described by the following summary statistics: arithmetic mean, standard deviation, median, minimum and maximum. These summary statistics will be presented by cohort for the original data as well as for the difference to baseline (defined as the pre-dose assessment of the day being analyzed).

Graphical displays of mean values with standard deviation will be included for absolute values as well as change from baseline. The number of subjects with at least one phosphate level > 5.5 mg/dL, with at least one phosphate level > 7 mg/dL and with at least one phosphate level > 9 mg/dL will be summarized using frequency tables.

The number of subjects with at least one value > 70 mg²/dL² of the product phosphate and calcium will be summarized using frequency tables.

The incidence of laboratory toxicities will also be summarized by worst CTCAE v4.03 grade and by treatment group and cohort. Frequency tables will also be provided for the changes of worst CTCAE v4.03 grade after start of treatment versus baseline.

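### Section 6.4.4 summarises ECOG performance status as a quantitative variable, and the planned statistics cannot show how many subjects worsened

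*SAP*

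**What the plan says.** Section 6.4.4 (Safety Parameters) of the current SAP supplement puts ECOG performance status in the same class as vital signs and ECG: "Quantitative data (vital signs, ECG, ECOG performance status) will be described by the following summary statistics: arithmetic mean, standard deviation, median, minimum, and maximum". It then extends these statistics to change: "These summary statistics will be presented by treatment group for the original data as well as for the difference to baseline". For plots it says: "Graphical displays of mean values with standard deviation will be provided".

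For the other class of data the section says: "Frequency tables will be provided for qualitative data". Section 4.1 (General Principles) has a similar general rule: "Frequency tables will be generated for categorical data". Because Section 6.4.4 names ECOG status as quantitative, neither rule clearly reaches it.

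The same section handles another graded scale differently. For CTCAE laboratory grades it plans: "Frequency tables will also be provided for the changes of worst CTCAE v4.03 grade after start of treatment versus baseline".

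The only other analysis of ECOG status is at baseline, in Section 6.1.3: "Variables include for example baseline ECOG Performance Status, number of target lesions, number of non-target lesions, cancer type, histology". SAP Version 1.0 has the same classification in its own Section 6.4.4 ("Quantitative data (vital signs, ECG, ECOG performance status) will be described by the following summary statistics"), and the supplement left it unchanged.

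**The concern.** ECOG performance status is a short ordered scale on which a higher grade means worse function. The SAP does not say this, but it is common knowledge. The distance between neighbouring grades has no fixed meaning, so a mean grade, a mean change or a mean-and-SD plot is hard to interpret. A gain in one subject also offsets a loss in another.

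The question a safety reader asks of this variable is how many subjects lost function, and by how many grades. That is a count. The SAP text commits to counts for laboratory grades, and even for phosphate, which is continuous (subjects above 5.5, 7 and 9 mg/dL). It commits to none for change in ECOG status. At stake is the clarity of one descriptive safety table.

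**Working it through.** The plan states no figure for ECOG status, so there is nothing to reproduce. The check is whether the five planned statistics determine the number of subjects who worsened.

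**Inputs.** Group size 20, the planned number of evaluable all-comer subjects at the MTD (Section 3). The SAP gives no distribution of ECOG change, so both distributions below are assumptions. Change is post-baseline minus baseline, and a positive value is a worsening.

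| Change in grade | Group A | Group B |
|---|---|---|
| -1 | 4 | 2 |
| 0 | 7 | 13 |
| +1 | 8 | 2 |
| +2 | 1 | 3 |
| Total | 20 | 20 |

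**Mean** = sum / 20.
- A: (-4 + 8 + 2) / 20 = 6/20 = 0.30
- B: (-2 + 2 + 6) / 20 = 6/20 = 0.30

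**SD** = square root of [(sum of squares - sum²/20) / 19].
- A: sum of squares = 4 + 8 + 4 = 16
- B: sum of squares = 2 + 2 + 12 = 16
- Both: square root of [(16 - 36/20) / 19] = square root of (14.2/19) = 0.865

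**Median.** The 10th and 11th ordered values are 0 in both groups, so the median is 0.

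**Minimum and maximum.** -1 and +2 in both groups.

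All five statistics of change agree. The counts do not:
- worsened by at least 1 grade: A 8 + 1 = 9 of 20 (45%); B 2 + 3 = 5 of 20 (25%)
- worsened by exactly 2 grades: A 1 of 20 (5%); B 3 of 20 (15%)

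The summary of the original scores need not separate the groups either. If every subject starts at grade 1 (a further assumption), each post-baseline score is 1 plus the change. Both groups then have mean 1.30, SD 0.865, median 1, minimum 0 and maximum 3. The mean-and-SD plots would also be the same.

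**The case against.** The strongest reply is that the plan does not rest on the mean alone. Suppose that 2 of 20 subjects worsen by two grades, 4 improve by one and 14 do not change. The mean change is (2×2 - 4×1)/20 = 0. The planned output would also give a minimum of -1, a maximum of +2 and an SD of square root of (12/19) = 0.79. A reader would see that someone lost two grades. This stands: it would be wrong to infer that the plan hides functional decline. What is lost is the count.

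A second reply is that Section 4.1 refers to standard table catalogues and Section 7 mentions table specifications, and neither is available here. They may contain an ECOG shift table. So the fair statement is that the SAP text does not commit to such a table, not that none will be produced.

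Two stronger readings are tempting and are not supported:

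- **Attrition.** A reader might infer that later means drift towards fitter subjects because those who decline stop treatment. The SAP does not establish this. Treatment may continue while the investigator assumes benefit, every subject has an end-of-treatment visit, and the SAP does not say when ECOG status is recorded. Such attrition would also distort frequencies tabulated by visit, so it is not a consequence of the quantitative classification.
- **Primary objective.** A reader might infer that the primary objective is compromised. Section 2 names safety and the MTD without mentioning functional status, and no endpoint or dose decision in the SAP uses ECOG status. Clinically reported decline may also appear in the adverse event tables of Section 6.4.3.

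Finally, in an open-label Phase I trial with descriptive summaries, part of this is reporting style. That limits the severity. It does not make means and SDs a good summary of an ordered scale.

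**Conclusion.** The point holds, at low severity. Section 6.4.4 classes an ordinal scale as quantitative and commits only to statistics that cannot show how many subjects worsened. In the assumed example that number is 9 or 5 of 20 with identical output, a difference of 20 percentage points. The example shows that the ambiguity is possible. It does not estimate its size in this trial, because the distributions were chosen for the purpose. The conclusion rests on the common understanding of ECOG status as an ordered scale and on the SAP text alone. It does not affect the MTD.

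**What to change.** Remove ECOG performance status from the list of quantitative data in Section 6.4.4. Add a frequency table of baseline against worst post-baseline score for each treatment group, with the number and percentage of subjects worsening by at least 1 and by at least 2 grades. State the denominator, for example subjects in the safety analysis set with a baseline score and at least one post-baseline score.

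The table has the same form as the change-in-worst-grade table already planned for CTCAE laboratory grades. The cost is a change of wording and one additional standard table. No new data are needed and no other analysis changes.

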Individual number of 21-day Cycles with continuous BAY 1163877 monotherapy (tablet) until disease progression or as long as clinical benefit is assumed by the investigator or until unacceptable toxicity occurs.

Note: Treatment with BAY 1163877 at MTD in Part 1 (expansion cohort “all comer”), Part 2 (expansion cohort sqNSCLC + LAC + BC + SCCHN), and Part 3 (expansion cohort

“Safety cohort” , sqNSCLC + LAC + BC) can run in parallel.

- Follow-up (FU)
 - End of Treatment (EOT) visit 0-14 days after last dose of BAY 1163877
 - FU visit at 30-35 days after dose of BAY 1163877

The first screening visit is scheduled within 7 days / 28 days before administration of the first dose of BAY 1163877. The informed consent form will be signed by the subject before or at the first screening visit. The screening period ends just before start of treatment.

The treatment period starts on the day of the first administration of study treatment on Cycle 1, Day 1 or on Cycle 1, Day -3 (“tablet bridging cohort” and “food effect assessment”) and ends with the last day when the study medication is administered in Cycle X. The length of treatment period may vary from subject to subject dependent on the number of individual treatment cycles. A Cycle for this study is defined as 21 days. There will be no break between cycles.

Statistical Analysis Plan

Protocol No.: **BAY 1163877/16443**

Page: 8 of 20:

When a subject starts new anti-cancer therapy, he / she is no longer considered “on study”.

An EOT visit will be performed for all subjects within 0-14 days after administration of the last dose of BAY 1163877. The FU visit for subjects who either discontinue prematurely or finish dosing with BAY 1163877 will be performed 30 - 35 days after the last study drug treatment. There will be no long-term (survival) FU period.

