Treatment: Subjects with PK assessment (all subjects of study Part 1 and 3 and at least 12 subjects of study Part 2 and approximately 8 subjects of the MTD expansion cohorts with impaired renal function at baseline) will receive BAY 1163877 (tablet or solution) on a continuous schedule starting with single-dose administration on Cycle 1, Day 1, followed by a “drugfree day” (to enable single dose PK assessments except for subjects in Part 3 who will receive BAY 1163877 twice daily continuously with no “drug free day”). Treatment with BAY 1163877 will resume on Day 3 of Cycle 1 if no protocol-defined dose-limiting toxicities (DLTs) are reported. Starting on Cycle 1, Day 3, the study drug will be self-administered twice daily for the remaining 19 days of Cycle 1. For subsequent cycles, study drug will be administered twice daily for 21 days until disease progression or as long as clinical benefit is assumed by the investigator or until unacceptable toxicity occurs.

In one of the dose escalation cohorts in study Part 1 (“tablet bridging cohort”), relative bioavailability of the tablet formulation will be assessed by administration of a single dose of the tablet formulation on Cycle 1, Day -3. Starting with Cycle 1, Day 1, subjects enrolled in the “tablet bridging cohort” will continue with the solution formulation as described above. Depending on the results from the relative bioavailability assessment, subjects who initially start with solution formulation may be switched to tablet formulation in later cycles.

Approximately 8 subjects enrolled in the MTD expansion cohorts (study Part 1 and Part 2) will receive single doses of BAY 1163877 on Cycle 1, Day -3, after consumption of a high-fat, high-calorie breakfast and on Cycle 1, Day 1, after an overnight fast of at least 8 hours followed by treatment according to the schedule described above starting on Cycle 1, Day 3.

Subjects without PK assessment in study Part 2 will receive BAY 1163877 (tablet or solution) twice daily from Cycle 1, Day 1 ongoing.

At home, subjects will document the intake of study drug in a diary.

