4.5 Data Rules

4.5.1 Baseline

Unless otherwise stated, baseline is defined as the last pre-dose assessment before first study drug administration or as the last pre-dose assessment before the time period being analyzed.

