6.3.2 Pharmacodynamic data

Cardiovascular parameters will be described by the following summary statistics: arithmetic mean, standard deviation, median, minimum and maximum. These summary statistics will be presented by cohort for the original data as well as for the difference to baseline (defined as the pre-dose assessment of the day being analyzed), if applicable.

Graphical displays of individual data as well as mean values with standard deviation may be included for absolute values as well as change from baseline.

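### SAP 6.4.4 takes change in phosphate, calcium and their product from the same day's pre-dose value, so the change tables and plots show only within-day movement

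*SAP*

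**What the plan says.** Section 6.4.4 (Safety Parameters) of the SAP supplement gives three laboratory variables their own treatment: "Calcium, phosphate and the product of calcium and phosphate will be described by the following summary statistics". The summaries are to be made by cohort "for the original data as well as for the difference to baseline (defined as the pre-dose assessment of the day being analyzed"). Mean graphs are planned for both the absolute values and the change. SAP Version 1.0 has the same definition, so the supplement left it as it was.

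The general rule in section 4.5.1 gives way to this one because it yields to any specific statement: "Unless otherwise stated, baseline is defined as the last pre-dose assessment before first study drug administration". The sentence then adds a second, period-specific alternative without saying when each applies.

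On dosing, section 3 says of subjects with PK assessment that "the study drug will be self-administered twice daily for the remaining 19 days of Cycle 1", starting on Day 3. Part 3 subjects, and Part 2 subjects without PK assessment, take the drug twice daily from Day 1. After that, "For subsequent cycles, study drug will be administered twice daily for 21 days", and "There will be no break between cycles". Tablet-bridging and food-effect subjects take their first dose on Cycle 1 Day -3.

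Section 6.3.2 (Pharmacodynamic data) uses the same reference for cardiovascular parameters, with a qualifier: "difference to baseline (defined as the pre-dose assessment of the day being analyzed), if applicable".

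**The concern.** A reader of a safety table headed change from baseline expects the change since before treatment. Under 6.4.4 the reference moves with each analysis day. Once dosing has started, that day's pre-dose sample already carries the effect of all earlier doses, and subtracting it removes that effect from the result.

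These are the only laboratory variables in 6.4.4 with their own summary statistics, graphs and thresholds, and safety is part of a primary objective. A flat change plot could be read as no drug effect in subjects whose phosphate had risen well above its starting level. The section also uses the word baseline in more than one sense: vital signs, ECG and ECOG status carry no same-day definition, and the CTCAE shift table compares the worst grade after start of treatment with a baseline that it does not define.

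**Working it through.** The plan states no figure that depends on this point, so there is nothing to reproduce. The check is an identity, followed by an illustration.

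**Notation**
- B: value before the first-ever dose
- P: pre-dose value on the day analyzed
- X: a later value on that same day

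**Identity**
- Planned change (6.4.4): X − P
- Change from pre-treatment: X − B = (X − P) + (P − B)
- Omitted by the plan: P − B, the shift accumulated up to that morning

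**When the two agree.** They agree when P = B. The design ensures this only on the first dosing day: Cycle 1 Day 1 for most subjects, Day -3 for tablet-bridging and food-effect subjects. For the latter two groups even the Cycle 1 Day 1 pre-dose value follows a dose.

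**When the planned change is zero.** If the pre-dose sample is the only one that day, X = P and X − P = 0. Whether such visits exist depends on the phosphate and calcium sampling times, which the SAP does not give.

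**Illustration.** Three values are assumed: B = 3.5 mg/dL, a within-day rise of 0.2 mg/dL, and calcium constant at 9.5 mg/dL. The pre-dose phosphate is set to each of the SAP's own thresholds in turn.

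| P (mg/dL) | X = P + 0.2 | Planned X − P | From pre-treatment X − B |
|---|---|---|---|
| 5.5 | 5.7 | 0.2 | 5.7 − 3.5 = 2.2 |
| 7 | 7.2 | 0.2 | 7.2 − 3.5 = 3.7 |
| 9 | 9.2 | 0.2 | 9.2 − 3.5 = 5.7 |

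Three subjects with very different rises have the same planned change. A different assumed B alters the last column by the same amount and leaves the planned column as it is.

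For the product at P = 7:
- before treatment: 3.5 × 9.5 = 33.25 mg²/dL²
- pre-dose: 7 × 9.5 = 66.5
- later that day: 7.2 × 9.5 = 68.4
- planned change: 68.4 − 66.5 = 1.9
- change from pre-treatment: 68.4 − 33.25 = 35.15

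**What is unaffected.** The summaries and graphs of absolute values and the subject counts (phosphate above 5.5, 7 and 9 mg/dL; product above 70 mg²/dL²) do not use the reference value.

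**The case against.** The strongest reply is that the signal stays in the report. For all three variables 6.4.4 also plans mean, SD, median, minimum and maximum of the original data, mean graphs of absolute values, and the threshold counts. A marked rise would appear in each. This stands, and it confines the defect to the change columns and change plots. It does not make them harmless. Subjects stay on treatment for differing numbers of cycles, so absolute means at later visits come from a changing group, and threshold counts give neither the starting level nor the size of the rise. The change from baseline is the quantitative within-subject summary, and it is the one that fails.

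A second reply is that a within-day difference may be intended, for instance on days with serial sampling. That would be a legitimate display, but then it should be labelled as such and should not be the only quantitative change given in the safety section.

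A third concerns scope. A reader might infer from 6.3.2 that cardiovascular safety changes are lost in the same way. The document does not support that: 6.4.4 separately summarizes vital signs and ECG against baseline with no same-day definition. Section 6.3.2 is an additional pharmacodynamic display, and the supplement added the words on applicability and made its graphs optional. Only its label needs attention.

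A fourth is that everything here is descriptive and that the numbers above are assumed. Both are true. The example shows how the definition behaves and does not estimate an effect in this trial.

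**Conclusion.** The definition in 6.4.4 is wrong as written for calcium, phosphate and their product. On every day after first dosing, the planned change omits the shift accumulated since before treatment. This follows from the definition and the dosing schedule and needs no outside data. The size of the omission equals that accumulated shift, which the SAP does not allow one to estimate.

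Three stronger readings do not hold:
- The rise does not disappear from the report, because the absolute summaries, graphs and counts keep it.
- The change is not zero at every visit. It is zero only where the pre-dose sample is the only one that day, and the sampling times are not in the SAP.
- Dose finding is not affected. No MTD estimate, DLT count or sample size uses this display.

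The correction should be made all the same, because the affected tables and plots concern the laboratory variables that the SAP singles out and would mislead if produced as specified.

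**What to change.** - **Section 6.4.4:** for calcium, phosphate and their product, define baseline as the last assessment before the first-ever dose of study drug, which means before Cycle 1 Day -3 for tablet-bridging and food-effect subjects. Use it for all change-from-baseline tables and plots of these variables.
- **Same-day difference:** if it is kept, show it separately under the label within-day change.
- **Section 6.3.2:** label the same-day difference for cardiovascular parameters as a within-day change as well. The vital-sign and ECG changes in 6.4.4 need no new definition.
- **Section 4.5.1:** the period-specific alternative need not be deleted, since it may serve other comparisons. Add only that it does not apply to these safety change tables.

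The cost is one derived baseline flag, relabelled displays and re-run tables and figures. No new data are needed.
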